7.1 Data and Safety Monitoring Plan

Safety data will be monitored on ***an ongoing basis*** by the Principal Investigator and captured by the Sponsor on the CRF. Appropriately trained personnel will be granted access to Express 5.4, the Electronic data capture system for this trial.

At least monthly, the Principal Investigator or designee will review vital signs (including at a minimum heart rate, systolic and diastolic blood pressure), adverse events (including all pre and post dosing adverse events), serum chemistry (including at a minimum alanine aminotransferase, aspartate aminotransferase, alkaline phosphatase, total bilirubin, blood urea nitrogen, and creatinine), coagulation (including at a minimum aPTT, PT, and INR), and urinalysis (including at a minimum urine protein (by dipstick), urine blood, and urine white blood cells). At least weekly, the Principal Investigator or designee will review hematology (at a minimum hemoglobin, absolute lymphocytes, absolute neutrophils, platelet count, WBCs) to advise on possible medication dose changes for safety reasons.

The Ionis Medical Advisor will answer queries and provide safety management recommendations to the Principal Investigator as needed. Anticipated AE's are fully described in the Investigator Brochure. Any safety issues identified in other apoC-III clinical trials will be promptly communicated by the Ionis to the Principal Investigator.

A monthly cumulative summary safety report for all apo-CIII studies, including the current study, will be issued by Ionis Pharmaceuticals, including an assessment of fatal cases, SAEs, treatment discontinuations, treatment-related AEs with severity and relatedness, laboratory analysis, ECG and vital signs. Particular attention will be paid to protocol defined monitoring/stopping rules. This report will be sent monthly to the Principal Investigator and will be used by the Data and Safety Monitoring Board (DSMB) for their ongoing data safety review.

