7.2.3 Evaluation of Adverse Events (Serious and Non-Serious)

The Investigator’s opinion of the following should be documented on the Adverse Event Case Report Form:

Relatedness

The event's relationship to the Study Drug (ISIS 304801 or placebo) is characterized by one (1) of the following:

- Related: There is clear evidence that the event is related to the use of Study Drug, e.g., confirmation by positive re-challenge test
- Possible: The event cannot be explained by the patient's medical condition, concomitant therapy, or other causes, and there is a plausible temporal relationship between the event and Study Drug (ISIS 304801 or placebo) administration
- Unlikely/Remote: An event for which an alternative explanation is more likely (e.g., concomitant medications or ongoing medical conditions) or the temporal relationship to Study Drug (ISIS 304801 or placebo) administration and/or exposure suggests that a causal relationship is unlikely (For reporting purposes, Unlikely/Remote will be grouped together with Not Related)
- Not Related: The event can be readily explained by the patient's underlying medical condition, concomitant therapy, or other causes, and therefore, the Investigator believes no relationship exists between the event and Study Drug

Severity

The event's severity is characterized by one of the following:

- Mild: The event is easily tolerated by the patient and does not affect the patient's usual daily activities
- Moderate: The event causes the patient more discomfort and interrupts the patient's usual daily activities
- Severe: The event is incapacitating and causes considerable interference with the patient's usual daily activities

If the event is an SAE, then all applicable seriousness criteria must be indicated.

Action Taken with Study Drug

Action taken with Study Drug (ISIS 304801 or placebo) due to the event is characterized by one of the following.

- None: No changes were made to Study Drug (ISIS 304801 or placebo) administration and dose
- Permanently Discontinued: Study drug was discontinued and not restarted
- Temporarily Interrupted, Restarted – Same Dose: Dosing was temporarily interrupted or delayed due to the AE and restarted at the same dose
- Reduced Dose: Dosing frequency was reduced

Treatment Given for Adverse Event

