7.4.2 Abnormalities of Laboratory Tests

Clinically significant abnormal laboratory test results may, in the opinion of the Investigator, constitute or be associated with an AE. Examples of these include abnormal laboratory results that are associated with symptoms, or require treatment, e.g., bleeding due to thrombocytopenia, tetany due to hypocalcemia, or cardiac arrhythmias due to hyperkalemia. Whenever possible, the underlying diagnosis should be listed in preference to abnormal laboratory values as AEs. Clinically significant abnormalities will be monitored by the Investigator until the parameter returns to its baseline value. The Investigator will consult with the Ionis Medical Advisor as needed, and for any exceptions to the above policy. Laboratory abnormalities deemed not clinically significant (NCS) by the Investigator should not be reported as AEs. Similarly, laboratory abnormalities reported as AEs by the Investigator should not be deemed NCS on the laboratory sheet.

The Investigator is responsible for reviewing and signing all laboratory reports. The signed clinical laboratory reports will serve as source documents.

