100K/mm ³ - 140K/mm ³	Weekly 300 mg study drug administration	Monitor every 1 week unless otherwise specified Obtain additional lab tests if 2 occurrences of platelet count 100 K/mm ³ -- 140K/mm ³ or 1 occurrence of platelet count ≤ 100K/mm ³ **
75K/mm ³ - 100K/ mm ³	Permanently reduce dose frequency to 300 mg every 2 weeks	Monitor every 1week unless otherwise specified Obtain additional lab tests if 1 occurrence of platelet count ≤ 100K/mm ³ **
50K/mm ³ - 75K/mm ³	If occurs while on dose of 300 mg every 2 weeks or 150 mg every week then permanently discontinue Study Drug, otherwise dose pause. When platelet count returns to >100K/mm ³ restart dosing at dose frequency of 300 mg every 2 weeks or 150 mg weekly ₁ (in consultation with the Ionis Medical Advisor as needed).	Monitor every 2-3 days until two successive values are > 75K/mm ³ then monitor every 1 week Consider discontinuation of antiplatelet/agents/NSAIDS/anticoagulant medication Obtain additional lab tests if 1 occurrence of platelet count ≤ 100K/mm ³ **
≤ 50 K/mm ³	Permanently discontinue Study Drug	Monitor daily until 2 successive values show improvement, then monitor every 2-3 days until 2 successive values are > 75K/ mm ³ . Patient should be evaluated by a hematologist to provide diagnostic and therapeutic management Steroids recommended*. It is strongly recommended that, unless the patient has a medical contraindication to receiving glucocorticoids, the patient receives glucocorticoid therapy to reverse the platelet decline. Monitor triglyceride levels weekly and continue AE monitoring during steroid therapy. Discontinue antiplatelet agents/NSAIDS/anticoagulant medication while platelet count <50K/mm ³ if

		possible Obtain additional lab tests if 1 occurrence of platelet count $\leq 100\text{K}/\text{mm}^3$ **
--	--	---

*Recovery in platelet count may be accelerated by administration of high dose steroids. Treatment guidelines for immune thrombocytopenia (Provan et al. 2010) recommend Dexamethasone 40 mg daily for 4 days every 2-4 weeks for 1-4 cycles; Prednis(ol)one 0.5-2 mg/kg/d for 2-4 weeks then taper; or Methylprednisolone 30 mg/kg/day for 7 days (**note:** may require continuation with oral steroids after methyl prednisolone)

**See Appendix J

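### The adverse event severity scale has no laboratory criterion, so a symptom-free platelet or ALT/AST value that permanently stops the drug is, read literally, Mild

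*Combined protocol and SAP*

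**What the plan says.** Section 7.2.3 asks for the investigator's opinion of severity for serious and non-serious events alike, on three levels, each defined by its effect on how the patient functions day to day:

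- The lowest level begins "Mild: The event is easily tolerated by the patient and does not affect the", with ordinary daily functioning as the yardstick.
- The middle level begins "Moderate: The event causes the patient more discomfort and interrupts the", with that yardstick again.
- The highest level begins "Severe: The event is incapacitating and causes considerable interference with the", likewise.

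Section 7.2.1 counts a clinically significant abnormal laboratory finding as an AE. Section 7.4.2 governs when a value becomes one: "Clinically significant abnormal laboratory test results may, in the opinion of the Investigator, constitute or be associated with an AE". Its examples are abnormalities with symptoms or needing treatment, and it adds: "Laboratory abnormalities deemed not clinically significant (NCS) by the Investigator should not be reported as AEs".

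Section 7.6 sets laboratory triggers for stopping, pausing or reducing treatment. The platelet table in 7.6.3 tells the investigator to "permanently discontinue Study Drug" at 50K/mm³ or less, and at 50–75K/mm³ if the patient is already on a reduced schedule or dose.

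Section 7.1 describes a monthly report, used by the DSMB, that includes "treatment-related AEs with severity and relatedness, laboratory analysis, ECG and vital signs".

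**The concern.** A severity grade should order events by how bad they are. This scale orders them by how the patient feels and functions. That suits injection-site reactions but not falling platelets, which may cause no symptoms until bleeding starts. Platelets are the laboratory signal already seen with this drug: section 2.3.4 reports a Phase 2 decrease, and section 6.4.5 requires weekly counts.

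Two things are at stake. First, anyone reading AEs by severity would find the most consequential platelet events in the lowest category. Second, values that change dosing without ending it might be recorded as AEs for one patient and not for another. Safety and tolerability is a secondary between-group outcome (section 4.2.2), but section 5.2 describes no safety analysis that would offset either weakness.

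**Working it through.** The plan gives no figure to reproduce, and the point does not rest on arithmetic. The check sets the severity definitions of 7.2.3 beside the dosing triggers of 7.6 and asks which grade each event would receive if the patient had no symptoms.

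| Event | Consequence under 7.6 | Grade under 7.2.3, read literally | Route to an AE record |
|---|---|---|---|
| Platelets 20,000/mm³, no bleeding | Permanent stop (7.6.3 text: below 25,000; table: 50K or less) | Mild | Classed as an AE for withdrawal in 7.8 |
| ALT 9 x ULN, confirmed, no other cause found | Permanent stop (7.6.1: above 8 x ULN) | Mild | Same |
| ALT above 5 x ULN, confirmed, lasting at least 2 weeks, no other cause found | Permanent stop (7.6.1) | Mild | Same |
| Platelets 50–75K/mm³ on 300 mg weekly, no bleeding | Pause, then restart on a reduced schedule or dose (7.6.3) | Mild, if recorded | Investigator's opinion (7.4.2) |
| Platelets 75–100K/mm³ | Permanent reduction in dose frequency (7.6.3 table) | Mild, if recorded | Investigator's opinion (7.4.2) |
| Injection-site pain that interrupts activities | No laboratory trigger | Moderate | Ordinary AE |

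1. Moderate needs more discomfort and interrupted activities, and Severe needs incapacity. An event with neither can only be Mild. The first five rows therefore share the lowest grade, although their dosing consequences range from a reduced frequency to a permanent stop.
2. The last row ranks above all of them. Section 2.3.4 says injection-site reactions were almost always mild, so this reversal is a property of the scale and not a forecast of frequent events.
3. The grade also feeds other records. Change in severity is one of the AE outcomes in 7.2.3, and a change in the intensity of an ongoing SAE is a trigger for a follow-up report in 7.3. A silent fall from 45K to 20K changes neither on this scale, though 7.3 also lists new information as a trigger.
4. No requirement in 7.2 or 7.4.2 makes a value an AE because it changed dosing. For the two rows that only pause or reduce dosing, recording rests on a judgement of clinical significance.

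**The case against.** The strongest reply is that the protocol separates severity, seriousness and action taken, and shows these events through the other channels. Much of that stands.

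- Section 7.8 places laboratory abnormalities that meet a stopping rule under its adverse event reason for withdrawal, and requires the reason for discontinuing treatment in the eCRF.
- Section 7.1 puts treatment discontinuations and laboratory analysis in the same monthly report and directs particular attention to the monitoring and stopping rules. Haematology is reviewed at least weekly.
- Section 7.2.1 names blood dyscrasias as an example of events that may be judged serious, and the AE form records the action taken with study drug.

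A reader might infer that platelet events are hidden from the DSMB, or never recorded as AEs. The documents do not support that. For permanent stops, 7.8 and 7.1 contradict it. For pauses and reductions, omission would require the investigator to judge a value that changes dosing not clinically significant, which is possible but not dictated.

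It is also fair to say that Mild is not compulsory. Severity is the investigator's opinion, and at 50K or less the table calls for daily counts, a haematologist's evaluation and recommended steroids, which could be judged to disrupt activities. But the grade then depends on the burden of management and not on the count, and the same count could be graded differently in two patients.

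None of these replies supplies a laboratory severity criterion or makes recording of a pause or reduction mandatory.

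**Conclusion.** The point holds as a defect in AE grading, with a smaller gap in AE capture. Read literally, 7.2.3 gives the lowest grade to symptom-free laboratory events that permanently stop the drug. The severity component of the monthly report then understates them, mainly for platelets. For values that only pause or reduce dosing, capture may be inconsistent.

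No numerical size can be given. A reader might take the planned 5 patients per arm and say that one regraded event moves a severe-event rate by 1/5, or 20 percentage points. That does not follow. Section 5.2 plans no AE severity table by arm, the only severity summary described is the monthly report covering all apoC-III studies, and the shift depends on which cut-point is mapped to Severe.

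A reader might also treat ALT as a main risk of this drug. Section 2.3.4 reports no hepatic laboratory signal, so ALT/AST serves here only as a second example of the missing criterion.

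The conclusion assumes that the event is recorded as an AE, that neither it nor its management disrupts daily activities, and that no laboratory grading scale sits outside the text read here, for example in the removed part of the risks section or in eCRF completion instructions.

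**What to change.** In 7.2.3, grade laboratory AEs by value. Add an explicit map from the protocol's existing cut-points (the platelet bands of 7.6.3 and the ALT/AST multiples of ULN in 7.6.1) to mild, moderate and severe. The sponsor should choose the map before any unblinded review. Keep the current scale for symptomatic events.

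In 7.4.2, state that any confirmed laboratory value that triggers a pause, reduction or stop under 7.6 is recorded as an AE whatever the symptoms.

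This changes recording only and no dosing rule. Separately, the actions for counts below 50,000/mm³ must be reconciled. For a first fall below that level after re-challenge, the 7.6.3 text provides for a hold and reconsideration, while other 7.6.3 text on reduced dosing and the table provide for permanent discontinuation. Grading by count does not depend on how that is settled.

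The cost is protocol and eCRF wording, a few more AE records, and a slightly less favourable severity summary.

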7.3 Reporting

Serious unanticipated problems and serious protocol deviations will be reported to the NIDDK/NIAMS IRB and Clinical Director as soon as possible but not more than 7 days after the PI first learns of the event. Not serious unanticipated problems will be reported to the NIDDK/NIAMS IRB and Clinical Director as soon as possible but not more than 14 days after the PI first learns of the event. Non-serious protocol deviations will be reported to the NIDDK/NIAMS IRB (as soon as possible but not more than 14 days after the PI first learns of the event) only if they represent a departure from NIH policies for the conduct of human subjects research, adversely affect the health care of the subject(s) or compromise the interpretation or integrity of the research. Non-serious protocol deviations that result from normal subject scheduling variations or technical issues associated with sampling that does not impact the health of the subject or the interpretation of the study data will not be reported.

For studies conducted under an IND, any event that is a serious, unexpected, and suspected adverse reaction (SUSAR) (related to study drug) will be reported by the Investigator to the NIDDK Clinical Director, NIDDK/NIAMS IRB, Food and Drug Administration (FDA), and Ionis Pharmaceuticals as soon as possible **and no later than 7 days** (for a death or life-threatening event) **or 15 days** (for all other SAEs) **after the investigator's or institution's initial receipt of the information.** All serious, unexpected, and suspected adverse reactions (SUSARS) will be reported in aggregate at the time of continuing review.

IND Safety Reports will be submitted to the FDA by NIDDK.

If only limited information is initially available, follow-up reports are required. If an ongoing SAE changes in its intensity or relationship to study drug or if new information becomes available, a follow-up SAE report should be sent to the FDA. All SAEs should be followed to resolution or stabilization.

Deaths will be reported by the investigative team to the NIDDK Clinical Director and NIDDK/NIAMS IRB within 7 days after the PI first learns of the event. All deaths that have occurred among study participants since the previous review will be summarized at the time of continuing review.

7.4 Procedures for Handling Special Situations

7.4.1 Contraception and Pregnancy

All patients of childbearing potential must refrain from sperm/egg donation and practice effective contraception from the time of signing the informed consent form until at least 3 months after their last dose of study treatment.

For the purposes of this study, women of childbearing potential are defined as any female who has experienced menarche, and who does not meet one of the following conditions:

- Postmenopausal: 12 months of spontaneous amenorrhea in females >55 years of age or, in females ≤55 years, 12 months of spontaneous amenorrhea without an alternative medical cause and FSH levels in the postmenopausal range for the laboratory involved
- 6 weeks after surgical bilateral oophorectomy with or without hysterectomy
- Post hysterectomy

For the purposes of the study, effective contraception is defined as follows:

For male patients:

- Effective male contraception includes a vasectomy with negative semen analysis at follow-up, or the use of condoms ~~together with spermicidal foam/gel/film/cream/suppository~~. Male patients must also encourage their female partner to use effective contraception from the time of signing the informed consent until 3 months after the patient's last dose of study treatment. Effective contraceptive for the female partner includes: surgical sterilization (e.g., bilateral tubal ligation), hormonal contraception, intrauterine contraception/device, or barrier methods (female condom*, diaphragm, sponge, cervical cap) ~~together with spermicidal foam/gel/film/cream/suppository~~. Male patients with partners that are pregnant must use condoms to ensure that the fetus is not exposed to the study drug.

For female patients:

- Using 1 or more of the following acceptable methods of contraception: surgical sterilization (e.g., bilateral tubal ligation), hormonal contraception, intrauterine contraception/device, or any 2 barrier methods (a combination of male or female condom* with diaphragm, sponge, or cervical cap) ~~together with spermicidal foam/gel/film/cream/suppository~~.

*Note: A female condom and a male condom should not be used together as friction between the two can result in either product failing.

If a patient becomes pregnant or a pregnancy is suspected, or if a male patient makes or believes that he has made someone pregnant during the study, then the Investigator must be informed immediately. An Initial Pregnancy Form should be submitted to Ionis or designee **within 24 hours** of first learning of the occurrence of pregnancy. Follow-up information including delivery or termination is reported on Follow-up Pregnancy Forms and reported within 24 hours.

Payment for all aspects of obstetrical care, child or related care will be the patient's responsibility.

Female patients: If a suspected pregnancy occurs while on the study (including follow-up), a pregnancy test will be performed. The patient with a confirmed pregnancy will be immediately withdrawn from treatment with Study Drug. However, the patient will be encouraged to complete the post-treatment follow-up portion of the study to the extent that study procedures do not interfere with the pregnancy. Regardless of continued study participation, the study physician will assist the patient in getting obstetrical care and the progress of the pregnancy will be followed until the outcome of the pregnancy is known (i.e., delivery, elective termination, or spontaneous abortion). If the pregnancy results in the birth of a child, the Investigator and Ionis or designee may require access to the mother and infant's medical records for an additional 8 weeks after birth.

Male patients: The progress of the pregnancy in a male patient's partner should be followed until the outcome of the pregnancy is known (i.e., delivery, elective termination, or spontaneous abortion). Male patients are not required to stop the study drug if their partner becomes pregnant. If the pregnancy results in the birth of a child, additional follow-up information may be requested for the mother and infant. Follow-up will be performed to the extent permitted by applicable regulations and privacy considerations.

7.4.2 Abnormalities of Laboratory Tests

Clinically significant abnormal laboratory test results may, in the opinion of the Investigator, constitute or be associated with an AE. Examples of these include abnormal laboratory results that are associated with symptoms, or require treatment, e.g., bleeding due to thrombocytopenia, tetany due to hypocalcemia, or cardiac arrhythmias due to hyperkalemia. Whenever possible, the underlying diagnosis should be listed in preference to abnormal laboratory values as AEs. Clinically significant abnormalities will be monitored by the Investigator until the parameter returns to its baseline value. The Investigator will consult with the Ionis Medical Advisor as needed, and for any exceptions to the above policy. Laboratory abnormalities deemed not clinically significant (NCS) by the Investigator should not be reported as AEs. Similarly, laboratory abnormalities reported as AEs by the Investigator should not be deemed NCS on the laboratory sheet.

The Investigator is responsible for reviewing and signing all laboratory reports. The signed clinical laboratory reports will serve as source documents.

